6.0 ANALYSIS POPULATIONS

The Transplanted Recipient Population will consist of all recipients who are transplanted according to the OCS™ Heart protocol and who have no major protocol violations. The analyses of all effectiveness and safety endpoints, except the rate of donor hearts utilization that were successfully transplanted after preservation and assessment on the OCS™ heart device, will be based on the Transplanted Recipient Population.

For this study, major protocol violations include:

- Donor and recipient's Inclusion/Exclusion Criteria Violation
- Failure to follow IFU
- Failure to follow protocol

The OCS™ Heart Population will consist of all donor hearts that are transported by the OCS™. The analysis of the rate of donor hearts utilization that were successfully transplanted after preservation and assessment on the OCS™ heart device will be based on the OCS™ Heart Population.

7.0 SUBJECT AND DONOR HEART DISPOSITION

The numbers of subjects in the following categories will be presented in Table 1.1:

- Signing the informed consent
- Not matched with an EXPAND heart
- Matched with an EXPAND heart
- Matched with an EXPAND heart turned down after OCS™
- Matched with an EXPAND heart accepted for transplant after OCS™ but not transplanted
- In the Transplanted Recipient Population

The table will also present the number and percentage of Transplanted Recipient Population patients who completed the study, who died on study, who withdrew from the study early, both overall and by time period (before day 30, between day 30 and 6 months, and between 6 months and 12 months), and the reason for withdrawal.

Donor heart disposition and acceptance details will be summarized in Table 1.2 for the OCS™ Heart Population using frequencies and percentages.

8.0 PROTOCOL DEVIATIONS

Protocol deviations will be summarized for the Transplanted Recipient Population by type of deviation and overall in Table 1.3 using counts and percentages.

9.0 DEMOGRAPHIC AND BASELINE CHARACTERISTICS

Recipient demographic and baseline characteristics will be summarized for the Transplanted Recipient Population in Table 2.1. Frequencies and percentages will be presented for gender, ethnicity, race, and blood type. Descriptive statistics will be presented for age, height, weight, body mass index, and panel reactive antibody. Recipient height and weight will also be summarized, stratified by gender, for the Transplanted Recipient Population in Supplemental Table 2.1.

Cardiac medical history (Table 2.2) and non-cardiac medical history (Table 2.3) at screening will be summarized for the Transplanted Recipient Population using descriptive statistics for continuous variables and frequencies and percentages for categorical variables.

Donor demographics, baseline characteristics, and inclusion criteria will be summarized in Table 2.4.1 for the Transplanted Recipient Population and in Supplemental Table 2.4.1 for the OCS™ Heart Population. Frequencies and percentages will be presented for gender, ethnicity, race, blood type, and donor inclusion criteria. Descriptive statistics will be presented for age, height, weight, and body mass index.

Inclusion-related donor demographic and baseline characteristics (Table 2.4.2) will be summarized by donor inclusion criteria for the Transplanted Recipient Population using descriptive statistics.

The number and percentage of subjects in each donor inclusion criterion group will be presented in Table 2.4.3 for the Transplanted Recipient Population.

Donor medical history will be summarized for the Transplanted Recipient Population in Table 2.5 and for the OCS™ Heart Population in Supplemental Table 2.5 using frequencies and percentages.

Donor cause of death (cerebrovascular hemorrhage, head trauma, or other), whether there was chest trauma, whether there was any evidence of sternum fractures, whether there was any evidence of rib fractures, whether there was any evidence of RV contusions, whether there was any evidence of LV contusions, whether the donor experienced cardiac arrest, and whether the cardiac arrest was witnessed will be summarized in Table 2.6 for the Transplanted Recipient Population and in Supplemental Table 2.6 for the OCS™ Heart Population using frequencies and percentages. The duration of cardiac arrest will be summarized using descriptive statistics.

Angiogram and donor management data at the final donor acceptance assessment will be summarized for the Transplanted Recipient Population in Table 2.7 and for the OCS™ Heart Population in Supplemental Table 2.7 using descriptive statistics for continuous variables and frequencies and percentages for categorical variables.

Final donor offer echocardiogram test results will be summarized for the Transplanted Recipient Population in Table 2.8 and for the OCS™ Heart Population in Supplemental Table 2.8 using descriptive statistics for continuous variables and frequencies and percentages for categorical variables.

Donor heart baseline chemistry test results will be summarized for the Transplanted Recipient Population in Table 2.9 and for the OCS™ Heart Population in Supplemental Table 2.9 using descriptive statistics.

10.0 OCS™ PRESERVATION CHARACTERISTICS

OCS™ perfusion time and ischemia time will be summarized using descriptive statistics in Table 3.1 for the Transplanted Recipient Population and in Supplemental Table 3.1 for the OCS™ Heart Population. Donor heart chemistry data on OCS™ instrumentation will be summarized by time point (pre-instrumentation, initial OCS™ instrumentation, and final OCS™ instrumentation) using descriptive statistics in Table 3.2 for the Transplanted Recipient Population and in Supplemental Table 3.2 for the OCS™ Heart Population. Donor heart assessment post OCS™ preservation will be summarized using frequencies and percentages in Table 3.3 for the Transplanted Recipient Population and in Supplemental Table 3.3 for the OCS™ Heart Population.

Device malfunction data will be summarized for the OCS™ Heart Population using frequencies and percentages in Table 3.4.

11.0 TRANSPLANT CHARACTERISTICS AND ICU AND HOSPITAL STAYS

Table 3.5 will summarize transplant characteristics for the Transplanted Recipient Population using descriptive statistics for continuous variables and frequencies and percentages for categorical variables.

Table 5.5 will summarize the post-transplant ICU stay for the Transplanted Recipient Population using descriptive statistics for the initial ICU stay and the re-admission ICU stay duration, and using the frequency and percentage for whether the recipient was readmitted to the ICU.

Table 5.6 will summarize the post-transplant hospitalization for the Transplanted Recipient Population using descriptive statistics for the initial hospital stay duration and the frequency and percentage for whether the recipient was re-hospitalized within the first 30 days post-transplant.

12.0 EFFECTIVENESS ANALYSES

All PGD based effectiveness endpoints will be based on the recipient adjudicated primary graft surveillance data.

12.1 Primary Effectiveness Analyses

The primary hypothesis for this study is that the true (success) proportion of transplanted patients meeting the primary effectiveness endpoint, patient survival at day 30 post-transplantation and absence of severe PGD (left or right ventricle) in the first 24 hours post-transplantation, is greater than the Performance Goal value of 0.65. The primary statistical hypotheses are as follows:

$$H_0: \pi \leq 0.65 \text{ and}$$

$$H_1: \pi > 0.65,$$

where π is the true proportion of transplanted recipients with patient survival at day 30 post-transplantation and absence of severe heart PGD (left or right ventricle) in the first 24 hours post-transplantation.

It is unlikely that there will be any missing data for the primary effectiveness endpoint. If there are no missing data, this endpoint will be summarized using counts and percentages and an exact 95% confidence interval for the true percentage based on the binomial distribution. A one-sided exact binomial test will be performed to test the null hypothesis H_0 .

If there are any missing data for this endpoint, it will be analyzed using multiple imputation methods to impute any missing data. Using SAS[®] PROC MI, the logistic regression method of imputation will be used with terms for various baseline characteristics (to be specified) and the primary endpoint. This method of multiple imputation is appropriate for a binary dependent variable with explanatory variables following a monotone missing pattern and assumes that the data for the dependent variable are missing at random (MAR). If the variables do not exhibit a monotone missing pattern, missing data will instead be imputed using the fully conditional specification (FCS) approach of SAS[®] PROC MI. Twenty imputation data sets will be generated. For each imputed dataset, PROC FREQ of SAS[®] will be used to obtain the success proportion and the corresponding standard error. PROC MIANALYZE of SAS[®] will be used to combine the results from the imputed datasets to produce an overall estimate of the true success proportion and the corresponding 95% confidence interval. The p-value for the test of the null hypothesis from a normal approximation test will also be presented. The results will be summarized in Table 4.1.1.

A site effect analysis based on the non-imputed data will be conducted to assess the poolability of data for the primary effectiveness endpoint. For this analysis, sites with fewer than five subjects will be grouped into a single, larger Analysis Site. A chi-square test will be performed to test the null hypothesis that the true proportion of transplanted patients meeting the primary effectiveness endpoint does not vary by site. A 0.15 significance level will be used for this test. If the p-value < 0.15, then an analysis adjusting for site will be considered. Table 4.1.2 will present the observed success proportion and corresponding exact 95% confidence interval for the true success proportion for each site.

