9. STATISTICAL METHODS

9.1. General

Continuous variables will be summarized using descriptive statistics, specifically the mean, median, standard deviation, minimum, and maximum. Categorical variables will be summarized using frequencies and percentages.

In the case of missing outcome data, a multiple imputation model will be used to present a complete outcome analysis.

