9.3. Analysis of Effectiveness Endpoints

9.3.1. Primary Effectiveness Endpoint

The primary hypothesis for this trial is that the true proportion of transplanted recipients with the composite of patient survival at Day 30 post-transplantation and absence of severe primary heart graft dysfunction (PGD) (left or right ventricle) in the first 24 hours post-transplantation is greater than the Performance Goal value of 0.65. The primary statistical hypotheses are as follows:

 H_0 : $\pi \le 0.65$ and H_1 : $\pi > 0.65$

where π is the true proportion of transplanted recipients with patient survival at Day 30 and absence of severe primary heart graft dysfunction (PGD) (left or right ventricle) in the first 24 hours post-transplant.

The primary effectiveness endpoint will be summarized using counts and percentages and an exact 95% confidence interval for the true percentage based on the binomial distribution. A one-sided exact binomial test at the 0.05 significance level will be performed to test the null hypothesis H₀. This endpoint will be analyzed using the transplanted recipient population.

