3.4 Determination of Sample Size

The sample size for this trial was determined based on the primary effectiveness composite endpoint of patient survival at Day 30 post-transplantation and absence of severe primary graft dysfunction (PGD) (left or right ventricle) in the first 24 hours post-transplantation. The primary statistical hypotheses to be tested are as follows:

$$H_0: \pi \leq 0.65 \quad \text{and}$$

$$H_1: \pi > 0.65,$$

where π is the true proportion of transplanted recipients with patient survival at day 30 post-transplantation and absence of severe PGD (left or right ventricle) in the first 24 hours post-transplantation. A one-sided exact binomial test will be performed to test the null hypothesis. The sample size calculations assumed an alpha level of 0.05, a Performance Goal of 0.65, a true primary endpoint proportion for OCSTM of 0.80, and power of 80%. Based on these specifications, the required sample size was determined to be 55 transplanted recipients. Assuming that there are exactly 55 transplanted recipients in the study, the null hypothesis will be rejected only if at least 76.4% (i.e., 42 of the 55 recipients) meet the primary endpoint. In order to increase the statistical power, the sample size was increased to 75 transplanted recipients.

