3.5 Changes to the Protocol-Specified Analyses

No changes were made to the protocol-specified analyses.

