5.3 Handling of Dropouts and Missing Data

If there are any missing data for the primary efficacy endpoint, multiple imputation methods will be used to impute missing data for this endpoint. No imputation will be performed for any other effectiveness or safety outcome.

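### Missing primary outcomes are imputed as a whole composite from unspecified baseline terms, without the 24-hour PGD result or a rule that an observed component failure settles the endpoint

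*SAP*

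**What the plan says.** The primary endpoint requires both survival at Day 30 and no severe PGD in the first 24 hours (Protocol 4.1, SAP 4.1). With complete data the test is exact: "A one-sided exact binomial test at the 0.05 significance level will be performed to test the null hypothesis" (Protocol 9.3.1).

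If the primary endpoint has missing values, SAP 12.1 switches to multiple imputation in which "the logistic regression method of imputation will be used with terms for various baseline characteristics (to be specified) and the primary endpoint". If the missing pattern is not monotone, fully conditional specification is used instead. Twenty imputed data sets are combined, and the p-value comes from a normal approximation. SAP 5.2 likewise names only baseline covariates, still to be specified. The same part of SAP 12.1 assumes data missing at random and calls missing primary data unlikely.

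On scope, Protocol 9.1 says: "In the case of missing outcome data, a multiple imputation model will be used to present a complete outcome analysis". SAP 5.3 limits this to the primary endpoint: "No imputation will be performed for any other effectiveness or safety outcome". SAP 3.5 nevertheless states: "No changes were made to the protocol-specified analyses".

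**The concern.** The two components become known at different times. Protocol 7.2 requires PGD surveillance in the first 24 hours at fixed times, with no visit window, and assesses survival at Day 30. The typical recipient with an incomplete composite is therefore one who left in between: PGD known, survival open. The planned model omits that PGD result, although severe PGD alone decides the endpoint. Omitting an observed variable that is this informative also makes the missing-at-random assumption harder to defend.

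The SAP does not say how a partly observed composite is coded. If it is treated as missing, a recipient who has already failed can receive an imputed success. If it is treated as failure when PGD is known to be severe, only recipients without severe PGD are imputed, and they are credited with too low a probability.

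There is also a reporting mismatch. Secondary endpoints 1 and 2 are the two components of the composite. SAP 5.3 bars imputation for them, so the rows of Table 4.1.1 could show an imputed composite beside components based on observed data only.

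**Working it through.** **Inputs from the documents.** SAP 3.4: "a Performance Goal of 0.65, a true primary endpoint proportion for OCSTM of 0.80, and power of 80" percent; one-sided exact binomial test; "the required sample size was determined to be 55 transplanted recipients", with rejection at 42 of 55; later increased to 75. Alpha is 0.05. The documents give no severe-PGD rate and no missingness rate, so the severe-PGD rate g is an assumption.

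**1. The plan's own figures.** The critical count is the smallest r with P(X ≥ r | 0.65) ≤ 0.05.
- n = 55: r = 42 (76.4%), exact alpha 0.0489, power at 0.80 of 0.8032. The stated design reproduces.
- n = 75: r = 56 (74.7%), exact alpha 0.0485, power 0.9003.

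The imputation method changes neither N nor these rejection counts.

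**2. PGD-free recipient with unknown Day-30 status.** With composite success 0.80, P(success | no severe PGD) = 0.80/(1 − g). A baseline-only model imputes about 0.80 on average.

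| assumed g | 0.80/(1 − g) | under-credit per recipient | points of 75 |
|---|---|---|---|
| 8% | 0.870 | 0.07 | 0.09 |
| 12% | 0.909 | 0.11 | 0.15 |
| 15% | 0.941 | 0.14 | 0.19 |

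Over a wider range for g of 5% to 20%, the conditional success rate runs from 0.842 to 1.000, so the under-credit runs from 0.04 to 0.20 of a recipient. The direction is against the device.

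**3. Recipient with known severe PGD and unknown Day-30 status, if coded missing.** The true value is 0 and the imputed value is about 0.80. The gain is 0.80k/75 for k such recipients: 1.07, 2.13 and 3.20 points for k = 1, 2 and 3.

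**4. Offset.** If partly observed composites are all coded missing and missingness is unrelated to PGD, the average correct value is g × 0 + (1 − g) × 0.80/(1 − g) = 0.80, which is what the model imputes. There is then no bias, only lost precision and individually impossible values. Bias arises when missingness is related to PGD.

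**5. Effect on the test.** Once any primary value is missing, SAP 12.1 uses the normal approximation. With complete data, and taking that test as one-sided with the standard error from the observed proportion:

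| count | exact p | normal-approximation p |
|---|---|---|
| 55/75 | 0.080 | 0.051 |
| 56/75 | 0.0485 | 0.027 |

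A worst-case illustration by simulation used 20 imputations, standard combining rules and an intercept-only model in place of the unspecified covariates:
- 55 successes, 19 other failures, one recipient with known severe PGD coded missing: median p = 0.033, below 0.05 in every run. Scored as a failure this is 55/75, with no missing data and exact p = 0.080.
- 54 successes, 19 other failures and two such recipients: median p = 0.040, below 0.05 in about 98% of runs. Scored as failures this is 54/75, exact p = 0.124.

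Part of each difference comes from the change of test, not from the imputed successes alone.

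**The case against.** The strongest reply is that the larger harm rests on a coding rule found nowhere in the SAP. A recipient with adjudicated severe PGD has failed the composite whatever happens by Day 30, so the endpoint is determined, and SAP 12.1 imputes only missing endpoint data. On that ordinary reading only step 2 remains, and it is small and conservative. This stands. A reader might infer that the plan will turn known failures into successes; the documents do not say so. They only fail to rule it out.

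A reader might also infer that PGD is always known when survival is not. That is too strong. PGD results are adjudicated (SAP 4.0), and right-ventricular PGD without an RVAD is diagnosed from hemodynamics, for which right-heart-catheter data are collected only as the centre's practice or a clinical cause provides (Protocol Appendices 1 to 3). PGD itself could be missing. In the other direction, Day-30 survival can often be recovered from the Month 6 and Month 12 contacts, by phone or record review (Protocol 7.3), which supports the SAP's view that missing primary data are unlikely.

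On scope, Protocol 9.1 is one general sentence that names no endpoint, so SAP 5.3 can be called a refinement. Secondary endpoints 1 and 2 are only summarised, with exact intervals and no test. The mismatch therefore has no bearing on the primary inference, but it sits badly with the SAP 3.5 statement that nothing changed.

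**Conclusion.** The point holds as a minor one. The imputation rule is composite-level, uses unspecified baseline terms, omits the 24-hour PGD result and leaves partly observed composites undefined.

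Its size depends on the coding. With known severe PGD scored as failure, PGD-free recipients are under-credited by about 0.07 to 0.14 of a recipient each (0.09 to 0.19 points of 75), assuming a success rate of 0.80 and severe PGD in 8% to 15%. With partly observed composites coded missing, each known-PGD recipient adds about 1.1 points. That is a bias only if missingness is related to PGD, and a loss of precision otherwise.

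It is tempting to take the step from 55/75 to 56/75, exact p 0.080 to 0.0485, as the decision margin. SAP 12.1 reserves the exact test for complete data, so the p-value to use with imputed data is the normal-approximation one. The simulated reversal shows what the open coding question could do near the threshold; it is not a forecast, because no missingness rate is given and little is expected.

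**What to change.** In SAP 5.2, 5.3 and 12.1:

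1. Score the composite as failure whenever either component is an observed failure (severe PGD in the first 24 hours, or death by Day 30).
2. Impute only the missing component. When Day-30 survival is missing, include the observed 24-hour PGD result among the predictors. Name the baseline covariates in the same edit.
3. Derive the composite and secondary endpoints 1 and 2 from the same component data, so that the rows of Table 4.1.1 agree.

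In SAP 3.5, declare that SAP 5.3 narrows the imputation scope of Protocol 9.1, or align the two texts.

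The cost is SAP wording and a few lines of code. No new data are needed, and N and the complete-data rejection rule stay as they are.

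### If a primary outcome is missing, does the SAP leave open which test decides the null hypothesis?

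*SAP*

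**What the plan says.** Protocol section 9.3.1 states the test without qualification: "A one-sided exact binomial test at the 0.05 significance level will be performed to test the null hypothesis". SAP section 3.4 also names the one-sided exact test with no condition on missing data. Protocol section 9.1 gives the rule for missing outcomes: "In the case of missing outcome data, a multiple imputation model will be used to present a complete outcome analysis". It names no test to go with the imputation.

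SAP section 12.1 has two branches. The first opens with "If there are no missing data, this endpoint will be summarized using counts and percentages and an exact 95% confidence interval", and the next sentence gives the exact test. The second opens with "If there are any missing data for this endpoint, it will be analyzed using multiple imputation methods to impute any missing data". Twenty data sets are imputed, and PROC FREQ "will be used to obtain the success proportion and the corresponding standard error" from each. PROC MIANALYZE pools them into an estimate and a 95% interval. The paragraph ends: "The p-value for the test of the null hypothesis from a normal approximation test will also be presented". The imputation covariates are still to be named, here and in SAP section 5.2.

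SAP section 3.5 declares: "No changes were made to the protocol-specified analyses". On the sample size, SAP section 3.4 first derives 55 recipients and then adds: "In order to increase the statistical power, the sample size was increased to 75 transplanted recipients".

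**The concern.** The protocol's exact test appears unconditional, yet in the SAP it sits under the complete-data condition. With one outcome missing, the only p-value that section 12.1 describes is a normal approximation after imputation, while section 3.5 says that nothing in the protocol's analyses has changed. A reader could ask which of the two decides the hypothesis. The SAP does not restate the side of the second test, list its covariates, or say how to score a recipient with one component known to have failed and the other missing.

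This is a single-arm trial with one primary hypothesis against a fixed goal of 0.65. Near the cutoff, the exact and approximate tests can give opposite conclusions on the same data. If the choice were open, it could be made after the results were seen, and the 0.05 level would not be assured.

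**Working it through.** **1. The plan's own figure.** Inputs from SAP section 3.4: goal 0.65, assumed rate 0.80, one-sided alpha 0.05. X is binomial.

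- n = 55: P(X ≥ 42 | 0.65) = 0.0489 and P(X ≥ 41 | 0.65) = 0.0874, so the cutoff is 42. Power P(X ≥ 42 | 0.80) = 0.803. The stated 55 and 42 of 55 reproduce.
- n = 75: P(X ≥ 56 | 0.65) = 0.0485 and P(X ≥ 55 | 0.65) = 0.080, so the cutoff is 56. Power is 0.900.

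**2. What the text settles.** The missing-data branch contains one p-value, and it is described as testing the null hypothesis. The alternative is π > 0.65, which makes the test one-sided; SAP section 5.1 sets 0.05. The standard error comes from each imputed data set, so it is sample-based. The composite requires survival and freedom from severe graft dysfunction together, so a known failure on either component already settles the outcome and leaves nothing to impute.

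**3. One close case.** n = 75, one missing, 55 successes among 74 observed. Suppose 15 of the 20 imputations fill in a success.

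- Pooled proportion: (55 + 15/20)/75 = 0.7433.
- Mean within-imputation variance, q(1 − q)/75: 0.002543.
- Between-imputation variance: (0.75 × 0.25/75²) × 20/19 = 0.0000351.
- Total: 0.002543 + (1 + 1/20) × 0.0000351 = 0.002580, so SE = 0.0508.
- z = (0.7433 − 0.65)/0.0508 = 1.84, one-sided p = 0.033: reject.
- Exact test on the 74 observed: P(X ≥ 55 | 0.65) = 0.057: do not reject.

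Had the outcome been known, the exact test would reject with a success (56/75, p = 0.0485) and not with a failure (55/75, p = 0.080). At the observed rate, 55/74 = 0.743, a success is the likelier result. Here imputation agrees with the more probable complete-data decision, and the observed-case exact test does not.

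**4. Size and power.** Assumptions: missing completely at random, no predictive covariates, 20 imputations, Beta(s + 0.5, f + 0.5) draws (s and f are the observed successes and failures), Rubin's variance, reject if z > 1.645. The numbers missing are assumed, since the documents give no rate. Entries are for 1/2/3 missing.

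| | n = 75 | n = 55 |
|---|---|---|
| Imputation test, size at 0.65 | 0.057/0.066/0.064 | 0.059/0.070/0.068 |
| Exact test on observed, size at 0.65 | 0.033/0.039/0.046 | 0.031/0.038/0.046 |
| Imputation test, power at 0.80 | 0.911/0.920/0.910 | 0.823/0.840/0.824 |
| Exact test on observed, power at 0.80 | 0.858/0.872/0.884 | 0.726/0.749/0.772 |

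Read as two-sided at 0.05, the imputation test has size 0.031 to 0.042 across both sample sizes.

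**5. How often a missing outcome must occur to matter.** Averaging over trials with none or one missing, the level passes 0.05 when the chance of a missing outcome exceeds:

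- n = 75: (0.05 − 0.0485)/(0.0569 − 0.0485) = 0.18.
- n = 55: (0.05 − 0.0489)/(0.0587 − 0.0489) = 0.11.

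**6. Agreement with the complete-data decision, one missing.** Chance of a different decision:

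| | Imputation test | Exact test on observed |
|---|---|---|
| n = 75, rate 0.65 | 0.8% | 1.6% |
| n = 75, rate 0.80 | 1.1% | 4.2% |
| n = 55, rate 0.65 | 1.0% | 1.8% |
| n = 55, rate 0.80 | 1.9% | 7.7% |

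**The case for a change.** The strongest case for a change is that a pivotal single-arm trial should have one deciding test, fixed in advance and exact, as the protocol says. Under the natural reading, the imputation test exceeds 0.05 in every missing-data case in the table. It can also be generous near the cutoff. With two missing and 54 of 73 observed, about 98% of imputation sets reject, whereas complete data would reject only if both missing recipients were successes, with probability (54/73)² = 0.547. Because the trial is unblinded, details left open could be settled after the data are seen.

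Part of this stands. The SAP does not restate the side of the second test, list the covariates, or reconcile its missing-data branch in so many words with the unconditional test in Protocol section 9.3.1 and its own section 3.4. The excess in size is real under the stated assumptions. With two or three missing at a true rate of 0.65, the observed-case exact test agrees with the complete-data decision more often than imputation does, so the advantage in step 6 is not general.

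It does not stand that nothing says which result decides. Section 12.1 directs the analyst by an explicit condition, and the protocol's own rule for missing outcomes is imputation, so section 3.5 is not clearly contradicted. Nor is the alternative free. It would demote an analysis that the protocol asks for and drop undetermined recipients from the test. It would also treat a recipient with unknown graft-dysfunction status as a failure if dead by Day 30 but exclude that recipient if alive. Exclusion would then depend on outcome, to the device's disadvantage, and the power figures above do not include that effect.

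**Conclusion.** No change to the plan is needed. With complete data, which the SAP expects for an endpoint known by Day 30, the exact test decides and nothing is in doubt. With a missing outcome, the natural reading is that the imputation p-value tests the hypothesis, one-sided at 0.05 with a sample-based standard error. The remaining omissions are details that an analyst fills sensibly from the alternative hypothesis and the composite's definition; the covariate list is ordinary analysis detail.

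What remains is a modest excess in size at the planned 75: 0.057 to 0.066 with one to three missing, against 0.0485 for the exact test on complete data. Predictive covariates would shrink it. Averaged over trials with none or one missing, it takes the level past 0.05 only if a missing outcome has more than about an 18% chance, and no document suggests such a rate. The one substantive alternative is a trade-off: with one missing it costs about 5 points of power at 75 (0.911 to 0.858) and about 10 at 55 (0.823 to 0.726), and it departs from the complete-data decision more often. These figures rest on data missing completely at random, no predictive covariates and twenty imputations.
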